6.1.1. Cell Line Selection

ALVR105 cell lines will be selected for each patient based on an overall HLA match with 2 shared alleles set as a minimum threshold as outlined below. The HLA alleles used for evaluation of matching are HLA-A, HLA-B, HLA-DR, and HLA-DQ. The same cell line should be used for all infusions.

The appropriate drug product (ie, the cell lines for infusion) for patient administration will be selected

6.1.2. Study Intervention Administration

At, or close to the time of administration, the product will be thawed at 37°C. As soon as the product has thawed completely, each vial will be wiped with an alcohol swab and the appropriate volume of study treatment will be removed from the vial or vials using a 16-gauge blunt-ended needle and 5 mL syringe. Study treatment is to be infused into the patient within 30 minutes of thawing. If the location of the patient is remote from the clinical site's cell storage facility, the thawing of the cryovials and preparation of infusion syringes should be conducted in an appropriate location for cell preparation that is sufficiently close to the patient to ensure that no more than 30 minutes elapse between the completion of thawing and infusion. See the Cell Handling Manual for further information.

Patients will be monitored according to institutional standards for the administration of blood products and, at a minimum, according to the following requirements:

- Patients in an outpatient setting must remain in the clinic for ≥1 hour after the end of the infusion.
- Patients must remain on continuous pulse oximetry for ≥30 minutes after the end of the infusion.
- Vital signs will be monitored at the end of infusion, and at 15, 30, 45, and 60 minutes after the end of the infusion.

All findings must be recorded in the electronic Case Report Form (eCRF).

Patients will receive supportive care for acute or chronic toxicity, including blood components, antibiotics, or other interventions as appropriate per local treatment guidelines. See [Section 6.8.2](#) for additional information. If possible, ALVR105 and intravenous immunoglobulin (IVIG) should not be administered on the same day.

6.2. Preparation/Handling/Storage/Accountability

1. The Investigator or designee must confirm appropriate temperature conditions have been maintained during transit for all study treatment received and any discrepancies are reported and resolved before use of the study treatment.
2. Only patients enrolled in the study may receive study treatment and only authorized site staff may supply or administer study treatment. All study treatments must be stored in a

secure, environmentally controlled, and monitored (manual or automated) area in accordance with the labeled storage conditions with access limited to the Investigator and authorized site staff.

3. The Investigator, institution, or the head of the medical institution (where applicable) is responsible for study treatment accountability, reconciliation, and record maintenance (ie, receipt, reconciliation, and final disposition records).
4. Further guidance and information for the final disposition of unused study treatment are provided in the Cell Handling Manual.

6.2.1. Study Drug Preparation and Dispensing

ALVR105 (and placebo) will be supplied in cryovials, which are to be transported from liquid nitrogen storage at the clinical site to the cell-thawing and preparation location in a liquid nitrogen Dewar or other suitable container. Details of the cell thawing, preparation for dosing, and administration to the patient will be provided to clinical sites in the Cell Handling Manual.

6.2.2. Storage and Accountability

ALVR105 (or placebo) is stored in the vapor phase of liquid nitrogen in a continuously monitored storage freezer.

After investigational medicinal product (IMP) accountability and reconciliation procedures have been followed, all material containing ALVR105 (or placebo) will be treated and disposed of as hazardous waste in accordance with governing regulations and clinical site procedures.

ALVR105 and placebo accountability are the responsibility of the Principal Investigator and Sponsor. However, this responsibility may be delegated to a suitably qualified Investigator who has had appropriate study-specific training that has been documented. The Sponsor will maintain records that will allow anonymous traceability of each ALVR105 cell line to the third-party PBMC donor from whom it originated. These records will be maintained for 30 years after expiry for each cell line.

Detailed records will be maintained to allow for accurate accountability of ALVR105 and placebo as per applicable Sponsor and clinical site procedures. For further details and specifications, see the Cell Handling Manual.

[REDACTED]

[REDACTED]	[REDACTED]
------------	------------

[REDACTED]

[REDACTED]

6.4. Study Intervention Compliance

Study patients are dosed at the site. They will receive study intervention directly from the Investigator or designee, under medical supervision. The date and time of each dose administered in the clinic will be recorded in the source documents and eCRF. The dose of study intervention and study participant identification will be confirmed at the time of dosing by a member of the study site staff other than the person administering the study intervention.

6.5. Dose Modification

This section is not applicable.

6.5.1. Retreatment Criteria

No further treatment is planned after the last dose of ALVR105 (or placebo) after Week 14. Patients will continue in the study for evaluation of safety, efficacy, and other endpoints after Week 14 for an additional 3 months (through Week 26).

6.6. Continued Access to Study Intervention after the End of the Study

No further treatment will be provided after the last dose of ALVR105 (or placebo) after Week 14. However, patients will continue in the study for evaluation of safety, efficacy, and other endpoints for an additional 12 weeks (3 months).

6.7. Treatment of Overdose

For this study, any dose of ALVR105 greater than any dose over the IRT assigned dose (2×10^7 for patients < 40 kg or 4×10^7 cells for patients ≥ 40 kg) within a 24-hour period (± 1 hour) will be considered an overdose.

As there is no antidote, the Sponsor does not recommend specific treatment for an overdose. In the event of an overdose, the Investigator should:

- Contact the Medical Monitor immediately.
- Evaluate the patient to determine, in consultation with the Medical Monitor, whether study treatment should be interrupted or whether the dose should be reduced.
- Closely monitor the patient for any AE/SAE and laboratory abnormalities until the next dosing day.
- Document the quantity of the excess dose as well as the duration of the overdose.

6.8. Concomitant Therapy

Clinically available (ie, not investigational) antiviral agents prescribed for other infections, such as foscarnet and ganciclovir to treat CMV, are allowed. Data on their use will be collected along with other concomitant medications.

6.8.1. Excluded Medications and/or Procedures

All patients may receive available supportive therapy with approved treatments. Investigators should try to maintain stable treatment to the extent possible.

Receipt of other investigational antiviral treatments (eg, brincidofovir or anti-BK virus monoclonal antibodies) within 28 days prior to randomization and throughout the duration of the study is prohibited.

Treatment with supportive regimen therapies, other intravesicular agents for the control of bleeding (including, but not limited to, aminocaproic acid), antispasmodics, treatment for pain control (including opioids), and blood product transfusion support are permitted. Analgesic use will be collected on a daily basis. Clinically available (ie, not investigational) antiviral agents prescribed for other infections are allowed. Use of cidofovir or brincidofovir (eg, for the treatment of AdV) must be discussed with the Medical Monitor prior to initiation. All instances of the use of any antiviral agents during the study will be recorded in the eCRF (including the drug name, dose, and

duration of treatment).

T cell ablative therapies, such as antithymocyte globulin, alemtuzumab (Campath-1H), or other immunosuppressive T cell-targeted monoclonal antibodies, are prohibited during the course of the study. Daily doses of corticosteroids exceeding 0.5 mg/kg prednisone (or equivalent) are prohibited during the course of the study. Should patients require medically a higher dose of steroids, no further study drug will be administered until the steroids are tapered to a dose equivalent of 0.5 mg/kg prednisone (or equivalent) or less.

6.8.2. Restricted Medications and/or Procedures

6.8.2.1. Supportive care

The following supportive care measures are permitted:

- Analgesics
- Narcotics
- IV hydration
- Antispasmodics
- Transfusion of red blood cells (RBCs)
- Transfusion of platelets
- Transfusion of fresh frozen plasma

All supportive care measures must be documented in the patient study records and the eCRF.

6.8.3. Documentation of Prior and Concomitant Medication Use

All medications, including GVHD prophylaxis, used within 30 days before screening will be recorded. All concomitant medications and concurrent therapies will be documented as indicated in the SoA ([Section 1.3](#)). Dose, route, unit frequency of administration, indication for administration, and dates of medication will also be captured in source documents and on the appropriate eCRF.

6.8.4. Rescue Medication

This section is not applicable.

7. DISCONTINUATION OF STUDY INTERVENTION AND PARTICIPANT DISCONTINUATION/WITHDRAWAL

7.1. Discontinuation of Study Intervention

The following criteria do not necessitate withdrawal from the study, but do render the patient ineligible to receive any additional infusions of study treatment:

1. Development of irreversible, life-threatening, Grade 3 to 4 acute GVHD within 6 weeks, or a Grade 3 to 4 non-hematologic AE within 4 weeks from last ALVR105 dose that is considered related to study treatment administration. If this occurs, the patient's toxicities will be followed until resolution or until the patient's participation in the study ends.
2. Receipt of any other hematopoietic stem cell product.
3. Receipt of therapy for relapse of the patient's primary malignancy.
4. Occurrence of Grade 3 or 4 CRS that persists beyond 72 hours. If this occurs, the patient's toxicities will be followed until resolution or until the patient's participation in the study ends.

If any of the above criteria are met, every effort should be made to keep the patient in the study and continue follow-up.

7.1.1. Temporary Discontinuation

Temporary discontinuation will be allowed only if discussed with and approved by the Medical Monitor.

7.1.2. Rechallenge

This section is not applicable.

7.2. Participant Discontinuation/Withdrawal from the Study

Participation of a patient in this clinical study may be discontinued for any of the following reasons:

- The patient withdraws consent
- The patient requests discontinuation from the study for any reason
- Occurrence of any medical condition or circumstance that exposes the patient to substantial risk and/or does not allow the patient to adhere to the requirements of the protocol
- Any SAE, clinically significant AE, severe laboratory abnormality, intercurrent illness, or other medical condition that indicates to the Investigator that continued participation is not in the best interest of the patient
- Pregnancy
- Requirement for prohibited concomitant medication
- Patient failure to comply with protocol requirements or study-related procedures

- Termination of the study by the Sponsor or the regulatory authority

If the participant withdraws consent for disclosure of future information, the Sponsor may retain and continue to use any data collected before such a withdrawal of consent.

If a participant withdraws from the study, he/she may request destruction of any samples taken and not tested, and the Investigator must document this in the site study records.

Patients who are discontinued from the study for any reason will not be replaced. Patients who discontinue the study early, should have the procedures scheduled for the Week 26/ET visit completed at the time of discontinuation from the study. The reason for patient withdrawal must be documented in the eCRF.

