7.3. Early Termination

The ET Visit will be performed for all patients who are prematurely discontinued up to Week 26 from the study; however, patients who decide only to discontinue therapy early will continue to complete trial procedures as per protocol. It is very important to ensure that all procedures, as outlined in the SoA ET visit, are performed in such patients at this visit prior to discontinuing the patient from the trial. Most importantly, a plasma sample for AdV, BKV, CMV, HHV-6, and JCV and a PCMB sample for EBV for PCR testing at the central laboratory should be collected at this visit.

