8.5.5. Pregnancy

- Details of all pregnancies in female participants will be collected after the start of study intervention and until 90 days after the last dose of study intervention.
- If a pregnancy is reported, the Investigator will record pregnancy information on the appropriate form and submit it to the Sponsor within 24 hours of learning of the [female participant or female partner of male participant (after obtaining the necessary signed informed consent from the female partner)] pregnancy.
- While pregnancy itself is not considered to be an AE or SAE, any pregnancy complication or elective termination of a pregnancy for medical reasons will be reported as an AE or SAE.
- Abnormal pregnancy outcomes (eg, spontaneous abortion, fetal death, stillbirth, congenital anomalies, ectopic pregnancy) are considered SAEs and will be reported as such.
- The patient will be followed to determine the outcome of the pregnancy. The Investigator will collect follow-up information on the participant and the neonate and the information will be forwarded to the Sponsor.
- Any post-study pregnancy-related SAE considered reasonably related to the study intervention by the Investigator will be reported to the Sponsor as described in [Section 8.5.4](#). While the Investigator is not obligated to actively seek this information in former study participants, he or she may learn of an SAE through spontaneous reporting.
- Any female participant who becomes pregnant while participating in the study will discontinue study intervention.

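### Protocol 7.2 lets pregnancy or need for a prohibited medication end study follow-up, where other sections only stop or hold infusions; later infections in such patients would not be observed

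*Protocol*

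**What the plan says.** Protocol 7.2 introduces its list with "Participation of a patient in this clinical study may be discontinued for any of the following reasons". Pregnancy is on the list, and so is "Requirement for prohibited concomitant medication". The wording permits and does not require. What it ends is participation, not dosing alone. At exit the section asks for one visit: "Patients who discontinue the study early, should have the procedures scheduled for the Week 26/ET visit completed at the time of discontinuation". No later visit is specified.

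Other sections handle the same events as dosing matters. On pregnancy, 8.5.5 says: "Any female participant who becomes pregnant while participating in the study will discontinue study intervention". On corticosteroids above 0.5 mg/kg prednisone equivalent, 6.8.1 says: "Should patients require medically a higher dose of steroids, no further study drug will be administered until the steroids are tapered". The list of T cell ablative therapies in 6.8.1 ends "or other immunosuppressive T cell-targeted monoclonal antibodies, are prohibited during the course of the study", but that section gives no dosing rule for a patient who needs one, and the four criteria in 7.1 do not include it.

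Two sentences protect follow-up. In 7.1, "every effort should be made to keep the patient in the study and continue follow-up", which is tied to that section's own four criteria. In 7.3, "patients who decide only to discontinue therapy early will continue to complete trial procedures as per protocol".

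The SAP covers the open-label cohort only. It analyses efficacy in all dosed patients (3.2.2), as observed and in general without imputation (3.1.5). It summarizes the per-patient infection count descriptively, with no stated rule for patients who leave before Week 14 (3.4.1).

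**The concern.** For pregnancy or high-dose steroids, one investigator could stop or hold infusions and keep following the patient, while another could take the patient off study. Both would be within the protocol.

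The second course stops observation of the endpoint, plausibly in patients whose risk of infection is raised. Protocol 2.2 says that infection risk depends on the degree of immunosuppression. Protocol 2.3.2 reports that donor-derived virus-specific T cells do not persist at methylprednisolone doses of 1 mg/kg/day or more. A patient who needs a prohibited immunosuppressant is therefore not an obviously random loss.

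The protocol itself can also put a patient in this position. Section 2.3.2 offers methylprednisolone 1 to 2 mg/kg/day for severe inflammatory reactions attributed to ALVR105. Appendix 7 gives 2 mg/kg for Grade 3 to 4 cytokine release syndrome (CRS) that does not improve after tocilizumab. If methylprednisolone and prednisone are taken as equal mg for mg (an assumption), both exceed the 0.5 mg/kg limit and so fall within the wording of 7.2.

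**Working it through.** **Step 1. The rules side by side.**
- Pregnancy: 7.2 permits study exit; 8.5.5 stops study intervention only.
- Steroids above 0.5 mg/kg: prohibited by 6.8.1, so 7.2 permits study exit; 6.8.1 itself only holds infusions until taper.
- T cell ablative therapy: prohibited by 6.8.1, so 7.2 permits study exit; it has no dosing rule of its own. Footnote l to the treatment-period schedules partly covers its use for GVHD: it bars further infusions for new Grade >2 or worsening GVHD. For patients discontinued on that ground it asks for follow-up to resolution of symptoms, not through Week 26.

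**Step 2. Does any other text withdraw the 7.2 permission?**
- 7.1: its keep-in-study sentence refers to its own criteria, which include neither pregnancy nor prohibited medication.
- 7.3: covers patients who choose to stop therapy, not those withdrawn by someone else.
- Schedule footnote n: keeps patients who have developed a viral infection on study. It does not cover those still free of infection, whose first infection is what would be missed.
- 4.1: states a general intention to follow all patients through Week 26, but 7.2 is the specific withdrawal rule.

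None of these removes the permission.

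**Step 3. What one exit loses.** Inputs are from the schedules for patients aged 12 or over, counting after Day 1 and assuming that the visit in the exit week is completed. Viral loads in Weeks 1 to 14: 14. Infection assessments in Weeks 1 to 14 plus Weeks 18, 22 and 26: 14 + 3 = 17.
- Exit at Week 4: 14 − 4 = 10 of 14 viral loads lost (71%); 17 − 4 = 13 of 17 assessments lost (76%).
- Exit at Week 8: 14 − 8 = 6 of 14 (43%); 17 − 8 = 9 of 17 (53%).
- Exit at Week 12: 14 − 12 = 2 of 14 (14%); 17 − 12 = 5 of 17 (29%).

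Under age 12 only adenovirus is scheduled weekly, so the viral-load counts differ for the other viruses. An infection present at the early termination visit would still be captured. After exit, investigators need not actively seek adverse events (8.5.1), and the later telephone call collects mortality only (4.4).

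**Step 4. Effect on the open-label mean.** The cohort is 25 to 35 patients, and the count has a maximum of 6 per patient (SAP 3.4.1). If a leaver stays in the denominator, each missed infection lowers the mean by 1/35 = 0.029 to 1/25 = 0.040. The ceiling for one patient is 6/35 = 0.17 to 6/25 = 0.24.

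**Step 5. How many patients?** The documents do not say. The nearest figure is from CHARMS (Protocol 2.2.2.1), where 1 of 58 patients is reported with systemic steroids restarted for skin GVHD in the weeks after infusion: 1.7%, exact 95% CI 0.04% to 9.2%. Applied to 25 to 35 patients, that gives 25/58 = 0.4 to 35/58 = 0.6 cases. No dose is given, and 6.8.1 would handle a high dose by a hold, so this is context and not a withdrawal rate. No frequency is given for T cell ablative therapy.

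**The case against.** The strongest reply is that the evidence and the benefit fall in different places. The no-imputation rule and the missing early-exit rule come from a SAP limited to the open-label cohort, and SAP section 1 says those patients were already enrolled, treated and followed. Rewording 7.2 cannot recover their data. The randomized cohorts could benefit, but no SAP for them is supplied and much of the related protocol text is redacted. The SAP also bases its analysis on Protocol Amendment 4. The protocol text supplied has a different primary endpoint and appears to be older (an inference), so whether 7.2 is unchanged there cannot be checked. All of this stands, and it limits the claim.

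A second reply is that specific dosing rules already cover most cases: 8.5.5 for pregnancy, 6.8.1 for steroids, footnote l for GVHD, and footnote n for patients given an antiviral for a target virus. This stands in part. These rules make exit less likely, but they sit beside the permission without cancelling it. It would be going too far to read 7.2 as the only stated consequence of T cell ablative therapy, because footnote l covers part of its use for GVHD.

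Third, the percentages in Step 3 describe any dropout at those weeks, whatever the reason. That is correct: they give the loss per exit, not its frequency.

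A reader might extend the point to the non-compliance item in 7.2. The documents do not support this well. Site staff give every dose under supervision (6.4), so non-compliance largely means missed visits. Section 7.4 already deals with those, and a patient who refuses procedures yields no data on or off study.

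**Conclusion.** The point holds as a cheap improvement of modest priority. Section 7.2 allows follow-up to end for two reasons, pregnancy and need for a prohibited medication. Other sections treat the first, and the steroid part of the second, as grounds only to stop or hold infusions. Any patient withdrawn this way has no scheduled virology or infection assessment afterwards, so later infections would not be observed.

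In the open-label cohort such infections would probably go uncounted. This is an inference from the as-observed rule and the silence on early leavers. The disposition table (SAP 3.3.1) would show the exit and its reason but would not correct the count. In the randomized cohorts the loss would weaken an analysis meant to include every randomized patient (Protocol 9.3).

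A reader might infer that the open-label result is biased, or that exits will differ between the randomized arms because GVHD is a named product risk. The documents support neither as a finding. They give no count of such withdrawals, which may be zero, and no analysis plan for the randomized comparison. The loss is plausibly related to outcome, but its direction and size between arms cannot be derived.

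**What to change.** - In 7.2, remove pregnancy and prohibited medication as grounds for leaving the study.
- In 7.1, list pregnancy and T cell ablative therapy as reasons to stop infusions, and steroids above the limit as a reason to hold them as 6.8.1 describes.
- Extend the keep-in-study sentence of 7.1 to any discontinuation of study drug, with visits continued through Week 26.
- Leave non-attendance to the contact steps in 7.4.
- Keep study exit for withdrawal of consent or patient request, loss to follow-up, study termination, and the investigator's judgement that follow-up itself is against the patient's interest.

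The cost is a rewording of two sections with cross-references to 6.8.1, 7.4 and 8.5.5. The off-drug, on-study status already exists in the protocol (7.3 and schedule footnote c). The downside is a few more already-scheduled visits and blood draws in patients no longer receiving study drug.
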